Appendix 5. Toxicity Grading Scale for Severity of Adverse Events and Laboratory Abnormalities

The DAIDS Toxicity Grading Scale Version 2.1 dated July 2017 is available at the following location:

<https://rsc.niaid.nih.gov/sites/default/files/daidsgradingcorrectedv21.pdf>

Appendix 6. Management of Clinical and Laboratory Adverse Events

Appendix 7. eGFR Automated Calculators

Automated calculators are provided by the National Institute of Diabetic and Digestive and Kidney Diseases.

Adults:

<https://www.niddk.nih.gov/health-information/professionals/clinical-tools-patient-management/kidney-disease/laboratory-evaluation/glomerular-filtration-rate-calculators/ckd-epi-adults-conventional-units>

Adolescents:

<https://www.niddk.nih.gov/health-information/professionals/clinical-tools-patient-management/kidney-disease/laboratory-evaluation/glomerular-filtration-rate-calculators/children-conventional-units>

9. REFERENCES39

10. SOFTWARE40

11. SAP REVISION41

12. APPENDICES42

LIST OF IN-TEXT TABLES

Table 3-1. Analysis Visit Windows for Chemistry (Except for SCr), Hematology, and
Coagulation Laboratory Tests17

CCI [REDACTED]

Table 3-3. Analysis Visit Window for 8-Point Ordinal Scale Collected after Day 4417

LIST OF IN-TEXT FIGURES

Figure 1-1. Study Schema8

LIST OF ABBREVIATIONS

AE	adverse event
AKI	acute kidney injury
ALT	alanine aminotransferase
AST	aspartate aminotransferase
BLQ	below the limit of quantitation
BMI	body mass index
BUN	blood urea nitrogen
CI	confidence interval
CKD	chronic kidney disease
CMH	Cochran-Mantel-Haenszel
CoV	coronavirus
COVID-19	coronavirus disease 2019
CRF	case report form
CSR	clinical study report
DAIDS	Division of AIDS
DAVG	Time-weighted average change from baseline
DMC	data monitoring committee
ED	Emergency department
ESKD	end-stage kidney disease
ET	early termination
FAS	Full Analysis Set
Hb	Hemoglobin
HLT	high-level term
HLGT	high-level group term
ICH	International Conference on Harmonization (of Technical Requirements for Registration of Pharmaceuticals for Human Use)
IMV	Invasive mechanical ventilation
IV	Intravenous
IXRS	interactive voice or web response system
LLT	lower-level term
LOQ	limit of quantitation
MedDRA	Medical Dictionary for Regulatory Activities
PCR	polymerase chain reaction
PK	pharmacokinetics
PT	preferred term
PTM	Placebo to match
Q1, Q3	first quartile, third quartile
RDV	remdesivir
RRT	renal replacement therapy

SAE	serious adverse event
SAP	statistical analysis plan
SARS	severe acute respiratory syndrome
SBECD	sulfobutylether-beta-cyclodextrin
SCr	serum creatinine
SD	standard deviation
SI (units)	international system of units
SOC	system organ class
SpO ₂	oxygen saturation
TEAE	treatment-emergent adverse event
TFLs	tables, figures, and listings
ULN	upper limit of normal
US	United States
WHO	World Health Organization

1. INTRODUCTION

This statistical analysis plan (SAP) describes the statistical analysis methods and data presentations to be used in tables, figures, and listings (TFLs) in the clinical study report (CSR) for Study GS-US-540-5912. This SAP is based on the study protocol Amendment 3 dated 27 August 2021 and the electronic case report form (eCRF). This SAP will be finalized before data finalization and unblinding. Any changes made after the finalization of the SAP will be documented in the CSR.

1.1. Study Objectives

The primary objective of this study is as follows:

- To evaluate whether remdesivir (RDV) reduces the composite risk of death or invasive mechanical ventilation (IMV) through Day 29 in participants with severely reduced kidney function who are hospitalized for coronavirus disease 2019 (COVID-19)

The secondary objectives of this study are as follows:

- To evaluate whether RDV reduces the risk of death through Day 29
- To evaluate whether RDV reduces the risk of IMV through Day 29
- To evaluate the time to recovery (defined as satisfying category 1, 2, or 3 by an 8-point ordinal scale)
- To evaluate the effect of RDV on clinical status assessed by an 8-point ordinal scale at Day 15 and Day 29
- To evaluate the effect of RDV on renal replacement therapy (RRT)-free days (among those without end-stage kidney disease [ESKD]) through Day 29
- To evaluate the effect of RDV on recovery through Day 29
- To evaluate the safety and tolerability of RDV in participants with severely reduced kidney function who are hospitalized for COVID-19

CCI

█

[figure not shown]
█

[REDACTED]

1.2. Study Design

This is a Phase 3 randomized, double-blind, placebo-controlled, parallel-group, multicenter study evaluating the efficacy and safety of RDV therapy in participants with severely reduced kidney function who are hospitalized for COVID-19.

Figure 1-1. Study Schema

Approximately 1,116 eligible participants are planned to be randomized in a 2:1 ratio to receive RDV or saline as placebo, according to the following treatment regimen, in addition to standard of care therapy:

Treatment Group A (N = 744): IV RDV 200 mg on Day 1 followed by IV RDV 100 mg once daily from Day 2 up to Day 5

Treatment Group B (N = 372): IV saline as placebo on Day 1 followed by IV saline as placebo once daily from Day 2 up to Day 5

Randomization will be stratified by:

- ESKD requiring chronic dialysis
- High-flow oxygen requirement
- Region (United States [US] vs. ex-US)

All participants will be requested to continue assessments during study hospitalization and any subsequent re-hospitalization to the same institution during Days 1 through 29 and attend the Day 60 phone follow-up (whether hospitalized or as an outpatient).

The schedule of assessments is provided as an appendix ([Appendix 1](#)).

1.3. Sample Size and Power

A total of approximately 1116 participants are planned to be randomized in a 2:1 ratio to 2 groups (744 in the RDV group and 372 in the saline as placebo group).

This sample size achieves approximately 85% power to detect a hazard ratio of 0.70 at a two-sided alpha level of 0.05. In the sample size calculation, it is assumed that the event rate in the saline as placebo group is 35%. The hazard ratio and event rate in the saline as placebo group are based on the most conservative estimates of the primary endpoint (composite of all-cause mortality or IMV) and the key α -controlled secondary endpoint (all-cause mortality) through Day 29 among a subset of participants with eGFR < 60 mL/min in the Division of Microbiology and Infectious Diseases Protocol 20-0006 Adaptive COVID-19 Treatment Trial (ACTT)-1 (hazard ratio of 0.67 and placebo rate of 33%).

The sample size calculation was done using software EAST (Version 6.5, module for log-rank test given accrual duration [120 days] and study duration [149 days] and 1 interim analysis at 50% information fraction using the Lan-Demets approach with O'Brien-Fleming type spending function).

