2.2. DMC Analyses

Two formal DMC meetings were planned for this study and were specified in protocol Sections 8.2 and 8.10. The first meeting has occurred and was conducted after the first 100 participants completed the Day 29 assessment. The purpose of this meeting was to review safety data, including renal and hepatic toxicity. The second meeting was planned after 50% of participants completed the Day 29 assessment. The purpose of this meeting was to review safety and provide a formal evaluation of futility and efficacy. However, this analysis was not performed due to the stop of study enrollment prior to reaching 50% of planned enrollment.

In addition to the above mentioned 2 formal DMC analyses, the DMC was provided with blinded safety listings including Grade 3 or higher AEs and SAEs every week for the first 2 weeks after the first participant was enrolled followed by every 2 weeks thereafter.

All details on DMC analyses are documented in the approved DMC charter.

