2.4. Change from Protocol-Specified Analyses

The second formal DMC analysis was not performed due to the stop of study enrollment prior to reaching 50% of planned enrollment. The reason for stopping enrollment was that it became clear the study would not fully enroll in a reasonable timeframe even after implementing enrollment mitigation strategies. The decision to stop study enrollment was documented in the 16 December 2021 Study Management Team meeting minutes.

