3.1.2. Full Analysis Set

The primary analysis set for efficacy analysis is defined as the Full Analysis Set (FAS), which will include all participants who (1) are randomized into the study, and (2) have received at least 1 dose of study drug.

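### SAP 1.2–1.3, written after enrolment stopped below half of plan, still give 1116 participants, one interim and about 85% power as the only size and power, not marked as superseded

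*SAP*

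**What the plan says.** SAP 1.2 (Study Design) states: "Approximately 1,116 eligible participants are planned to be randomized in a 2:1 ratio to receive RDV or saline as placebo". It lists arm sizes of 744 ("Treatment Group A (N = 744") and 372. SAP 1.3 (Sample Size and Power) repeats these numbers and adds: "This sample size achieves approximately 85% power to detect a hazard ratio of 0.70 at a two-sided alpha level of 0.05". The stated inputs are a 35% placebo event rate and a calculation that includes "1 interim analysis at 50% information fraction".

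Later sections describe a different trial:

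- SAP 2.2, on the second formal DMC review: "However, this analysis was not performed due to the stop of study enrollment prior to reaching 50% of planned enrollment".
- SAP 2.4 repeats this ("The second formal DMC analysis was not performed due to the stop of study enrollment prior to reaching 50% of planned enrollment"), gives slow enrolment as the reason, and dates the minuted decision to 16 December 2021.
- SAP 3.9 says no alpha was spent, so the final test is at 0.05.
- SAP 6.4 merges the primary and final analyses because the study closed early with fewer participants than intended.

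The only count of actual participants in the visible text is in SAP 2.2, where the first DMC meeting was "conducted after the first 100 participants completed the Day 29 assessment".

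**The concern.** The SAP was revised for the enrolment stop: the interim was dropped, the alpha restored to 0.05, and two analyses merged. Its change sections record each of these. None records what the stop did to sample size or power. SAP 1.2–1.3 still use the present tense for 1116, carry no superseded label, and do not point to the sections that overtake them.

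SAP 3.5 keeps a confirmatory test of the primary endpoint at 0.05, with mortality tested only if the primary succeeds. A reader who wants to know what that test could detect finds only 85% power for a hazard ratio of 0.70. That figure belongs to a trial at least twice as large. It could be cited beside the result, and no output scheduled in the visible text corrects it: SAP 4.1 tabulates counts, not power or detectable effect.

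**Working it through.** **Inputs.** Hazard ratio (HR) 0.70, placebo Day 29 event rate 35%, two-sided alpha 0.05, 2:1 allocation and N = 1116 (SAP 1.3). Planned two-sided levels 0.0031 at the interim and 0.0490 at the end (Protocol 8.7, Table 5). No interim and final level 0.05 for the analysis as it will be run (SAP 3.5, 3.9).

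**Formulas.** Under proportional hazards, the remdesivir Day 29 risk is 1 − 0.65^HR, which is 0.2603 at HR 0.70. Expected events are D = (N/3) × 0.35 + (2N/3) × (1 − 0.65^HR). Schoenfeld power is Φ(√(2D/9) × |ln HR| − 1.96), with |ln 0.70| = 0.3567.

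**Step 1: reproduce the stated 85%.** At N = 1116, D = 372 × 0.35 + 744 × 0.2603 = 323.9. Then √(2 × 323.9/9) × 0.3567 = 3.026, and Φ(3.026 − 1.96) = 85.7%. With the planned interim (bivariate normal, 0.0031 then 0.0490) it is 85.6%. The stated figure reproduces.

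**Step 2: bound the enrolled number.** Half of 1116 is 558. Enrolment stopped before reaching it, so at most 557 were enrolled, taking the approximate target of 1116 as exact. The efficacy population in SAP 3.1.2 also requires dosing ("which will include all participants who (1) are randomized into the study, and (2) have received at least 1 dose of study drug"), so it cannot be larger than that.

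**Step 3: power at the bound, no interim.** At N = 557, D = 161.7. Then √(2 × 161.7/9) × 0.3567 = 2.138, and Φ(2.138 − 1.96) = 57.1%. The drop from Step 1 is 85.7 − 57.1 = 28.6 points.

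**Step 4: sensitivity to method, N = 557.**

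| Method | Power |
|---|---|
| Schoenfeld, remdesivir rate taken as 0.70 × 35% = 24.5% | 55.6% |
| Schoenfeld, proportional hazards | 57.1% |
| Two proportions | 59.2% |
| Simulated unstratified log-rank, 10,000 runs | 59.8% |
| Unpooled variance | 60.4% |
| Freedman, unequal allocation | 61.3% |

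The methods that give more at 557 also give more at 1116. The simulation gives 87.9% there, so its drop is 28.1 points.

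**Step 5: sensitivity to the design inputs, N = 557, Schoenfeld.** A 33% placebo rate gives 54.5% and 40% gives 63.0%. The HR of 0.67 with 33% that SAP 1.3 cites from the earlier trial gives 63.4%.

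**Step 6: smaller N.** The enrolled number is not in the documents, so the rows below 557 are assumptions. Events are recomputed under each detectable HR.

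| N | Events at HR 0.70 | Power at HR 0.70 | HR for 80% power | HR for 85% power |
|---|---|---|---|---|
| 557 | 161.7 | 57.1% | 0.62 (152 events) | 0.59 (149 events) |
| 500 (assumed) | 145.1 | 52.6% | – | – |
| 400 (assumed) | 116.1 | 44.1% | 0.56 | 0.53 |
| 300 (assumed) | 87.1 | 34.8% | 0.50 | 0.47 |

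The 100 participants at the first DMC meeting are a logical floor (about 15% power), not an estimate of enrolment.

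**The case against.** The strongest reply is that nothing here contradicts anything. SAP 1.2–1.3 call the size planned and describe a calculation that was done. The SAP rests on protocol Amendment 3, repeats that design, and puts departures in dedicated change sections. No rule uses the power figure, since the futility look was dropped. Precision will be visible from the HR with its 95% interval and the risk difference with its interval (SAP 6.1.3), and counts are scheduled (SAP 4.1). On this view the residue is a missing cross-reference.

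Much of this stands. The 85% is right for the plan it describes. A reader might infer that the power was miscalculated, that the SAP hides the stop, or that it implies 1116 were randomized. The documents support none of these: the figure reproduces, the stop is disclosed in four places, and the size is labelled as planned. Nor is the final test or its alpha compromised, because SAP 3.9 restores 0.05 for the right reason and the SAP does not say a null result would show no effect.

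What does not stand is that the change sections already cover the point. They replace the interim, the alpha and the analysis timing. They put nothing in place of the size or the power, so a reader of the whole SAP learns that the plan failed but not what power remains.

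**Conclusion.** The point holds as a superseded size and power left standing as the only ones stated, not as a calculation error. At the design assumptions, the stated 85% is about 28 points above what the largest enrolment compatible with the SAP would give on the same method. It is worth fixing, but the harm is limited: no test, endpoint, alpha or analysis set changes, and the results will show the precision achieved.

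Two further readings go too far. A reader might take 57% as the trial's actual power, but the enrolled number is not stated and 557 is only an upper bound. A reader might also take 57% as a strict ceiling, but it is one formula's value. The methods tried span 55.6% to 61.3% at N = 557, and other placebo rates or a stronger effect move it further (Step 5). None of these comes near 85%.

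The statement that no other size or power is given applies to the visible text, since the study schema figure is not shown and parts of the SAP are redacted. No allowance was made for dropout or for randomized participants who were never dosed; either would lower the power.

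**What to change.** Before the SAP is finalised and the data unblinded:

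1. In SAP 1.2–1.3, label 1116 (744/372), one interim and about 85% power as the original plan, superseded by the enrolment stop, with a pointer to SAP 2.4, 3.9 and 6.4.
2. State the total enrolled number, pooled over arms, with the nominal 2:1 ratio. By-arm counts are not needed, so blinding is not touched.
3. State the expected events and either the power or the detectable HR at the design assumptions with no interim. If 557 were enrolled, the detectable HR would be about 0.62 for 80% power and 0.59 for 85%. This uses design inputs only and is not post hoc observed power.

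If the SAP is already final, put the same statement in the clinical study report. SAP section 1 sends changes made after finalisation to that report. It does not expressly call for a note on power, but the report is the natural place for one.

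The cost is a few sentences. The downside is a less favourable stated figure.

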2. TYPE OF PLANNED ANALYSIS

2.1. Interim Analyses

Prior to the final analysis, interim analyses may be conducted, and the analyses may be submitted to regulatory agencies to seek guidance for the overall clinical development program.

2.2. DMC Analyses

Two formal DMC meetings were planned for this study and were specified in protocol Sections 8.2 and 8.10. The first meeting has occurred and was conducted after the first 100 participants completed the Day 29 assessment. The purpose of this meeting was to review safety data, including renal and hepatic toxicity. The second meeting was planned after 50% of participants completed the Day 29 assessment. The purpose of this meeting was to review safety and provide a formal evaluation of futility and efficacy. However, this analysis was not performed due to the stop of study enrollment prior to reaching 50% of planned enrollment.

In addition to the above mentioned 2 formal DMC analyses, the DMC was provided with blinded safety listings including Grade 3 or higher AEs and SAEs every week for the first 2 weeks after the first participant was enrolled followed by every 2 weeks thereafter.

All details on DMC analyses are documented in the approved DMC charter.

2.3. Final Analysis

The final analysis will be performed after all participants have completed or discontinued from the study, outstanding data queries have been resolved or adjudicated as unresolvable, and the data have been cleaned and finalized.

The analysis of the primary endpoint of all-cause mortality or IMV through Day 29 and the key α -controlled secondary endpoint of all-cause mortality through Day 29 will be conducted at the final analysis (see Section 3.5 for prespecified testing strategy). The overall Type I error rate will be controlled at the two-sided 0.05 significance level.

2.4. Change from Protocol-Specified Analyses

The second formal DMC analysis was not performed due to the stop of study enrollment prior to reaching 50% of planned enrollment. The reason for stopping enrollment was that it became clear the study would not fully enroll in a reasonable timeframe even after implementing enrollment mitigation strategies. The decision to stop study enrollment was documented in the 16 December 2021 Study Management Team meeting minutes.

3. GENERAL CONSIDERATIONS FOR DATA ANALYSES

Analysis results will be presented using descriptive statistics. For categorical variables, the number and percentage of participants in each category will be presented; for continuous variables, the number of participants (n), mean, standard deviation (SD) or standard error (SE), median, first quartile (Q1), third quartile (Q3), minimum, and maximum will be presented.

By-participant listings will be presented for all participants in the All Randomized Analysis Set and sorted by participant identification (ID) number, visit date, and time (if applicable). Data collected on log forms, such as adverse events (AEs), will be presented in chronological order for each participant. The treatment group to which participants were randomized will be used in the listings. Age, sex at birth, race, and ethnicity will be included in the listings, as space permits.

3.1. Analysis Sets

Analysis sets define the participants to be included in an analysis. Analysis sets and their definitions are provided in this section. Participants included in each analysis set will be determined before the study blind is broken for analysis. The analysis set will be identified and included as a subtitle of each table, figure, and listing.

For each analysis set, the number and percentage of participants eligible for inclusion will be summarized by treatment group.

A listing of reasons for exclusion from analysis sets will be provided by participant.

CCI

3.1.1. All Randomized Analysis Set

All Randomized Analysis Set includes all participants who were randomized in the study.

3.1.2. Full Analysis Set

The primary analysis set for efficacy analysis is defined as the Full Analysis Set (FAS), which will include all participants who (1) are randomized into the study, and (2) have received at least 1 dose of study drug.

3.1.3. Safety Analysis Set

The primary analysis set for safety analyses is defined as the Safety Analysis Set, which will include all participants who (1) are randomized into the study and (2) have received at least 1 dose of study drug.

CCI

CCI

3.1.7. Virology Analysis Set

The Virology Analysis Set will include all participants who (1) are randomized into the study, (2) have received at least 1 dose of RDV, and (3) have positive SARS-CoV-2 viral load at baseline (a result of “No SARS-CoV-2 detected” is considered as negative, results of Inconclusive, < limit of quantitation (LOQ) SARSCoV2 detected, and numerical results are considered as positive).

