8.3.1.2. Safety

The primary analysis set for safety analyses is defined as the Safety Analysis Set, which will include all participants who (1) are randomized into the study and (2) have received at least 1 dose of study treatment. Participants will be grouped according to the treatment which they received.

CCI

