3.2. Participant Grouping

For analyses based on the All Randomized Analysis Set and FAS, participants will be grouped according to the treatment to which they were randomized. For analyses based on Safety Analysis Set, CCI Virology Analysis Set and CCI participants will be grouped according to the actual treatment they received.

The actual treatment received will differ from the randomized treatment only when their actual treatment differs from randomized treatment for the entire treatment duration.

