Appendix 2. Programming Specifications

- 1) If the age from the Day 1 eCRF is not available, age will be calculated as follows:

Only year is provided for the date of birth (DOB). Use July 1 for the month and day.

- a) AGE (years) is calculated from the number of days between the DOB and Study Day 1,
- b) Use the SAS INTCK function to determine the number of “1st-of-month days” (eg, January 1st, February 1st, March 1st) between DOB and Day 1 (inclusive),
- c) Divide the result in (b) by 12,

AGE = the integer of the result in (c),

Age for laboratory test reference range will be based on the age at the sample collection date.

- 2) All screened participants refer to all participants who are screened (ie, with non-missing screening date) and have a screening number. For summaries the same participant is counted only once.
- 3) Screen failure participants are the participants who were screened and answered “No” for any inclusion criteria or “Yes” for any exclusion criteria regardless of which version of protocol the participant was consent to.
- 4) Participants in the randomized analysis set are defined as participants randomized into the study. IXRSRAND is the source to determine whether the participant is randomized (ie, participant with non-missing RGMNDTN in the IXRSRAND dataset), and confirmed by the eCRF ENROLL dataset (ie, ENROLLYN = “Yes” in ENROLL dataset).
- 5) Randomized treatment (ie, TRT01P in ADSL) is derived from IXRSRAND, while actual treatment received (ie, TRT01A in ADSL) is assigned as the randomized treatment if participant took at least 1 dose of study drug and assigned as blank if the participant was never dosed.
- 6) In the disposition table, the reasons for premature discontinuation are displayed in the order as they appear on the eCRF.

- 7) Body mass index (BMI)

BMI will be calculated only at baseline as follows:

$$\text{— BMI} = (\text{weight [kg]}) / (\text{height [meters]}^2)$$

Baseline height and weight will be used for this calculation if available

8) TEAE

Events with Missing Onset Day and/or Month

An event is considered treatment emergent if all of the following 3 criteria are met:

- i. The month and year (or year) of onset date is the same as or after the month and year (or year) of the first dose of study drug, and
- ii. The month and year (or year) of the onset date is the same as or before the month and year (or year) of the 30th day after the date of the last dose of study drug, and

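### SAP Appendix 2, item 5 sets actual treatment equal to randomised treatment for everyone dosed, so it cannot carry out the treatment-received grouping in SAP 3.2 and protocol 8.3.1.2

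*SAP*

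**What the plan says.** **Grouping by treatment received.** Protocol 8.3.1.2 says of the Safety Analysis Set: "Participants will be grouped according to the treatment which they received". SAP 3.2 repeats this for the Safety Analysis Set, the Virology Analysis Set and some redacted sets: "participants will be grouped according to the actual treatment they received". It then limits when the two treatments may differ: "The actual treatment received will differ from the randomized treatment only when their actual treatment differs from randomized treatment for the entire treatment duration".

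**Programming rule.** SAP Appendix 2, item 5 takes the randomised treatment (TRT01P) from the randomisation system. It says that the actual treatment (TRT01A) "is assigned as the randomized treatment if participant took at least 1 dose of study drug", and leaves it blank if the participant was never dosed. SAP 7.6 declares no departure from the protocol's safety analyses.

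**Virology Analysis Set.** SAP 3.1.7 requires randomisation and then adds: "2) have received at least 1 dose of RDV, and (3) have positive SARS-CoV-2 viral load at baseline". The FAS in SAP 3.1.2 asks instead that participants "have received at least 1 dose of study drug", and the Safety Analysis Set in SAP 3.1.3 uses the same dosing condition. For all sets, SAP 3.1 says: "Participants included in each analysis set will be determined before the study blind is broken for analysis". It also says that for each set "the number and percentage of participants eligible for inclusion will be summarized by treatment group".

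**The concern.** SAP 3.2 and item 5 give different definitions of the same variable. SAP 3.2 has a working exception for someone who received the other arm's product from first dose to last. Item 5 has no exception. A programmer who follows item 5 produces safety tables by randomised treatment, limited to those dosed, under a label that promises treatment received. A reader of the adverse event and laboratory tables could not tell which rule had been applied. Anyone mis-dosed for the whole course would be counted in the wrong arm.

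A second, weaker point lies in SAP 3.1.7. Its dosing condition names RDV, not study drug. Taken literally, it shuts out every correctly dosed placebo participant. If any between-arm virology comparison used this set, that comparison would have no control arm.

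**Working it through.** The plan states no figure on this point, so the check sets the rules side by side and then bounds the effect.

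**Step 1: dosing patterns under each rule.** PBO is saline placebo. The last column is the RDV-dose condition of SAP 3.1.7 taken alone.

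| Randomised | Received | SAP 3.2 | Item 5 | Meets 3.1.7 dose condition |
|---|---|---|---|---|
| RDV | RDV throughout | RDV | RDV | yes |
| PBO | PBO throughout | PBO | PBO | no |
| RDV | PBO throughout | PBO | **RDV** | no |
| PBO | RDV throughout | RDV | **PBO** | yes |
| PBO | one RDV dose, rest PBO | PBO | PBO | yes |
| RDV | one PBO dose, rest RDV | RDV | RDV | yes |
| RDV | never dosed | not assigned | blank | no |

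The rules disagree in two rows only. Those are the two cases in which SAP 3.2 lets actual treatment depart from randomised treatment. Item 5 therefore fails in exactly the cases the exception exists to catch, and agrees everywhere else.

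**Step 2: arm sizes the documents imply.** The planned split reproduces: 1116 × 2/3 = 744 RDV and 1116 / 3 = 372 placebo.

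- Upper bound: SAP 2.4 says enrolment stopped before 50% of plan. 0.5 × 1116 = 558 was not reached, so at most 557 were randomised. At 2:1, placebo is 557 / 3 = 185.7, about 186.
- Lower bound: SAP 2.2 says the first DMC meeting followed Day 29 completion by 100 participants, so at least 100 were randomised. At 2:1, placebo is 100 / 3 = 33.3, about 33.

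**Step 3: effect of one participant.** Let x of n in the placebo arm have an event, and move one participant out.

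- If that person had the event, the proportion changes by x/n − (x − 1)/(n − 1) = (n − x)/[n(n − 1)]. This is largest at x = 1, where it equals 1/n.
- If not, it changes by x/(n − 1) − x/n = x/[n(n − 1)]. This is largest at x = n − 1, where it again equals 1/n.

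So the change is at most 1/186 = 0.54 percentage point at the upper bound and 1/33 = 3.0 points at the lower.

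**Step 4: the virology set.** If everyone is dosed as randomised and is positive at baseline, the planned maximum under SAP 3.1.7 as written is 744 RDV and 0 placebo. With study drug in place of RDV it would be 744 and 372. At the upper enrolment bound, the placebo participants left out number about 186 or fewer. Under SAP 3.2, the only way to be in this set and grouped as placebo is to have had an RDV dose in error (fifth row).

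**The case against.** **On item 5.** The governing rule is already stated correctly in SAP 3.2 and the protocol, and item 5 is one programming line beneath it. The SAP 3.2 sentence, with its word *only*, could be read as a limit that does not require the two treatments ever to differ. The rules agree for correct, mixed and absent dosing, and whole-course mis-dosing may not have occurred. The last argument stands as a limit on size. The others do not remove the conflict: grouping by treatment received has no meaning if the variable always equals the randomised treatment, and item 5 is the only visible derivation.

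**On SAP 3.1.7.** A reader might infer that placebo participants were dropped from the virology analyses by mistake. Some visible text points that way:

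- Sets are fixed before unblinding, although an RDV-dose test needs the treatment code.
- Summarising and grouping a one-drug set by treatment is redundant.
- The protocol's Biomarker set (8.3.1.4) is open to both arms.
- Protocol 6.8 collects swabs from all participants.
- Appendix 2, item 28 models DAVG on treatment.

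The documents do not support the inference as an error. The use of this set and SAP 3.1.4 to 3.1.6 are redacted, and the analyte and analysis set behind the DAVG code are not shown. The rules in 3.1 are generic, and a set with no placebo members can still be tabulated. Protocol 5.1.2 allows virology staff who select samples for resistance analysis to be unblinded, so people holding codes could apply the test. An RDV-only purpose remains possible, and no visible objective or end point is virological. What stands is a question for the sponsor.

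**Conclusion.** Item 5 is wrong as written. It conflicts with SAP 3.2 and protocol 8.3.1.2, no redaction affects that conflict, and SAP 7.6 does not record it as a change. It is minor. It matters only for a participant given the other arm's product for the entire course, and the documents report none. The 0.5 to 3 point range illustrates one hypothetical participant. It assumes exact 2:1 allocation, and neither 186 nor 33 is a reported arm size. The primary and key secondary analyses use the FAS by randomised treatment and do not change.

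Two stronger readings should be resisted. A reader might infer that the safety tables did misclassify someone; nothing in the documents shows that. A reader might also infer that SAP 3.1.7 reduces in practice to being randomised to RDV and dosed. That follows only if its RDV-dose condition is programmed from TRT01A, which no visible text says.

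The wording of SAP 3.1.7 remains a query, not a finding of error.

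**What to change.** **Item 5.** Reword it so that TRT01A defaults to the randomised treatment for anyone dosed, unless dosing records show that the other treatment was received for the entire course, as SAP 3.2 provides. Leave it blank if never dosed.

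The sponsor should confirm which record identifies the product given: the Study Drug Administration eCRF named in SAP 3.8.1, or the unblinded pharmacy or dispensing records. Protocol 5.6 has sites log participant and lot numbers for investigational drug vials, but those logs are held at the sites. The documents do not show that lot data reach the analysis database. Placebo is ordinary saline (protocol 5.2.1), and it is not clear that its use is logged in the same way. The wording change costs one line; whether extra data must be obtained is not shown.

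**SAP 3.1.7.** The sponsor should state whether the set serves any between-arm comparison. If it does, replace RDV with study drug in the dosing condition. If it is meant to be RDV-only, say so there and align SAP 3.1 and 3.2. Either way the cost is a wording change.
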